Multicenter RCTs should be conducted in children and adults to determine the benefits or harms of calcitriol or vitamin D analogs in patients with CKD G3a to G5; patient-level outcomes including falls, fractures, sarcopenia, muscle strength, physical function, progression to end-stage kidney disease, cardiovascular events, hospitalizations, and mortality should be assessed. Studies should also include patients with more severe SHPT and should determine the impact of reducing PTH to different target levels, such as the normal range versus higher levels.

KDIGO 2017 Clinical Practice Guideline Update for the Diagnosis, Evaluation, Prevention, and Treatment of Chronic Kidney Disease-Mineral and Bone Disorder (CKD-MBD)

In people with hyperparathyroidism secondary to CKD, does treatment with vitamin D or vitamin D analogues improve patient-related outcomes.

NICE guidelines 2021

In patients with CKD G3b-5, it is currently recommended to monitor the PTH every 3-6 month(3). As more than 50 % of the patients have elevated PTH already at CKD G3b, it is an everyday

consideration for the clinician if the patients should be treated to reduce PTH. This is both time- and cost consuming. At present, there is no evidence to advise if secondary hyperparathyroidism should be treated in patients with CKD.

To improve our knowledge about when secondary hyperparathyroidism should be treated, we want to conduct a randomized clinical trial with one group of patients being treated if PTH is elevated versus a second group of patients not being treated if PTH is elevated.

Hypothesis

We hypothesize that suppression of initially elevated PTH will improve BMD, arterial stiffness, muscle mass and muscle strength in patients with CKD.

Methods and Materials

Subjects will be recruited from the patient population in the outpatient clinic at the Department of Nephrology at Herlev and Gentofte Hospital, Herlev, Denmark.

Study population

Inclusion criteria (all four needs to apply)

1. ≥ 50 years of age at screening
2. CKD G4-5nonD (eGFR < 30 mL/min/1.73m 2) based on local laboratory assessment of serum creatinine and eGFR estimated by the CKD-EPI formula)
3. Plasma PTH $>$ upper normal limit of local laboratory reference range ($> 8,5\mu\text{mol/L}$) and/or treated with active vitamin D (Alphacalcidol) or calcimetics (Cinacalcet) initially
4. Written informed consent

Exclusion criteria

1. Patients who have received a kidney transplant

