2. Patients receiving treatment with specific anti-osteoporosis medication (denosumab/bisphosphonates) (because of the profound effect on calcium/phosphate fluxes and BMD)

Withdrawal from intervention but continued follow-up (included in intention-to-treat analysis)

1. Withdrawal of consent
2. Kidney transplantation

3. Parathyroidectomy
4. Necessity to initiate dialysis treatment

Patients may withdraw from both intervention and follow-up at any time if desired.

Study design

The REPAIR-CKD trial will be an investigator-initiated pragmatic randomized controlled clinical trial. Included patients will be randomized 1:1 into one of two treatment arms with different targets levels for plasma-PTH: A liberal PTH target ($< 5 \times$ upper normal limit = 42,5 $\mu\text{mol/L}$) or an intensive PTH target (within interval of lower and upper normal limits = 2,0 – 8,5 $\mu\text{mol/L}$) (Figure 1). The cut-off for the liberal PTH target ($< 5 \times$ upper normal limit) was discussed in the national CKD-MBD group. It is chosen to allow the clinician initiate treatment if PTH reaches unusually high levels, no studies have focussed on PTH-targets before, consequently the cut-off is chosen as part of the pragmatic design.

The trial will also pilot the feasibility to obtain a difference in the PTH levels between treatment groups.

[figure not shown]

Figure 1. Visit overview.

Sample size

The primary outcome will be difference in the change in total hip BMD between treatment groups.

In an observational study, the decline in total hip BMD (g/cm^2) was $-1.19\%/\text{year}$ (men) and $-1.51\%/\text{year}$ (women). The decline in men is chosen for a conservative estimate (36). In the dialysis population, the standard deviation (SD) of the one-year decline in BMD is $\pm 5.2\%$ (37). The variance in the BMD change in dialysis patients is expected to be higher than in the CKD population, and therefore this is considered a conservative estimate. Based on these observations the expected decline in BMD in the liberal target group during 18 months is -1.8% (5.2%).

In a previous trial, alendronate was able to increase BMD in total hip by 2.8% during the first year of treatment and 3.4% during 2 years treatment, and thus to increase BMD by 3.1% in 18 months (38). We expect to obtain a similar effect in the intensive target group.

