A sample size of 70 participants is estimated ($\beta=0.10$; $\alpha=0.05$ (two-sided), drop out 20 % during the study) to detect a difference of 4.9 % change in total hip BMD (effect size) during 18 months.

To ensure that the trial can also provide information about the other fields of interest, we did some statistical considerations about these as well. A minimal relevant difference in the level of PTH after 18 months of intervention is expected to be a difference in PTH of 0.5 times the upper limit of normal range ($8.5 \mu\text{mol}/\text{L}$ (Atellica IM PTH)). PTH has a skewed distribution and thus log transformed to obtain normality. In a population of patients with CKD G4-5 the mean and standard deviation of the logPTH was 1.191 (0.380) (own data, not published). To obtain a difference of 4.25 $\mu\text{mol}/\text{L}$ in PTH = logPTH of 0.628 ($(\beta=0.10$; $\alpha=0.05)$ a sample size of 22 participants is estimated (including drop-out margin of 20%). Based on former studies the sample size should be sufficient to demonstrate a difference of 1 m/s in pulse wave velocity which is considered a difference of clinical relevance for future cardiovascular events(39).

Interventions

The trial is estimated to run for 24 months, as patients will be included during a 6-months period following 18 months follow-up. Following inclusion there will be a 4 weeks run-in period where patients will not be treated with active vitamin D or calcimetics. After run-in patients will be

randomized to either a liberal PTH target ($< 5 \times$ upper normal limit = 42,5 $\mu\text{mol/L}$) or an intensive PTH target (within interval of lower and upper normal limits = 2,0 – 8,5 $\mu\text{mol/L}$). In the intensive PTH target group, treatment will be initiated as soon as the PTH rise above the upper limit of normal. In the liberal PTH target group, treatment will not be initiated until PTH rise above five times the upper limit of normal.

PTH will be measured as intact PTH with Atellica IM PTH assay at Herlev Hospital laboratory (normal range 2,0 – 8,5 $\mu\text{mol/L}$).

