PTH is routinely measured in the clinic and blinding is not feasible as unblinding of the allocated treatment group will easily occur. The open-label design may influence the adherence, as the treating physician or the patient may favour a specific PTH target. It is therefore of great importance to monitor the adherence to the allocated treatment target through levels of PTH, and doctors as well as participants will be encouraged to comply.

The DXA-scan and analysis of this will be blinded, as the investigator performing the intervention will not perform the scans.

Efficacy endpoints

Primary endpoint:

Difference in % change in bone mineral density (BMD) between the treatment groups.

This is the generally accepted outcome for trials comparing treatment effects on BMD.

Secondary endpoints:

- Difference in follow-up BMD between treatment groups
- Difference in follow-up arterial stiffness between the treatment groups
- Differences in follow-up muscle mass between the treatment groups
- Differences in follow-up muscle function between the treatment groups
- Differences in bone histology between the treatment groups
- Differences in follow-up health-related quality of life between the treatment groups
- Differences in number of spinal fractures between the treatment groups

The feasibility to obtain a differential PTH level of at least 0.5 times the upper limit of normal between the two groups will be determined. During the piloting the number of withdrawals of consent and crossovers will be determined to improve the set-up, to increase retention and adherence and adjust the sample size estimation.

Adverse events

All serious adverse events (SAE) will be recorded during trial period. SAE is any case of death, life threatening event, persistent or significant disability, hospitalisation, prolongation of existing hospitalisation or treatment necessary to avoid the above and congenital anomaly/birth defect. It is the responsibility of the investigator to assess whether any SAE is with reasonable possibility causally related to the study intervention. Within 7 days after becoming aware of a SAE, the investigators will report these to the local scientific ethics committee. Once annually the primary investigator will report a summary of SAEs to the local scientific ethics committee.

All cases of hyper/hypocalcaemia and hyperphosphatemia will be registered as adverse events of interest.

Statistics

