All included participants will be accounted for and presented in a CONSORT diagram.

Baseline characteristics will be presented as mean \pm standard deviation or median and interquartile range, and number and percentages.

The primary endpoint % change in BMD during 18 months will be compared between groups with unpaired t-test.

This will be further explored by comparison of BMD after 18 months by ANCOVA adjusted for baseline BMD.

For secondary outcomes with a baseline and a single follow-up measurement, comparison between treatment groups will be performed by ANCOVA, adjusted for the baseline value. If more suitable, this analysis will be done with mixed effect model.

Secondary outcomes with baseline and multiple post-randomization measurements will be compared as baseline-adjusted follow-up values using a mixed model repeated measures approach.

Categorical outcomes will be compared by Chi²-test. Continuous outcomes will be presented as graphs of means and standard error of the means at each time point. Continuous outcomes with non-normal distribution will be logarithmic transformed to obtain normality before analysis.

Two-sided P-values < 0.05 is considered statistically significant.

All data will be described including data-incompleteness as well as reasons for data-incompleteness. Imputation will be used, if reasonable, to manage data-incompleteness in the analyses.

Analyses will be run in R studio, SAS and STATA. A statistical analysis plan will be decided before data lock.

Time schedule

The study will not be initiated until approved by the local scientific ethics committee, expected in summer of 2025. Recruitment is expected to last 6 months followed by 18 months follow-up. The study period will last 18 months for each patient.

Rights and publication

Principal investigator [name] will coordinate the study. [name] will be first author on any subsequent publications.

[name] will be final author on any subsequent publications.

Authorship will be granted to any person who contribute to the subsequent publications according to the Vancouver Guidelines.

All results, either positive, negative or inconclusive, will be submitted for publication in peer-reviewed journals.

Ethics

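### The PTH sample size takes the log of a difference (log10 of 4.25 = 0.628) as a difference of logs, so 22 participants do not give the stated 90% power

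*Protocol*

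**What the plan says.** The protocol's Sample size section sets the minimal relevant PTH difference at 18 months at 0.5 times the upper normal limit of 8.5, that is 4.25 in the units printed. It notes that PTH is skewed and is log-transformed, and reports that in a CKD G4-5 population "the mean and standard deviation of the logPTH was 1.191 (0.380) (own data, not published". It then writes the difference of 4.25 "in PTH = logPTH of 0.628" and concludes, for 90% power and alpha 0.05, that "a sample size of 22 participants is estimated (including drop-out margin of 20"%).

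The same gap returns under Efficacy endpoints: "The feasibility to obtain a differential PTH level of at least 0.5 times the upper limit of normal between the two groups will be determined". The Statistics section plans the analysis on the log scale: "Continuous outcomes with non-normal distribution will be logarithmic transformed to obtain normality before analysis".

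No expected PTH level is given for either arm. What is given is "an intensive PTH target (within interval of lower and upper normal limits" of 2.0 and 8.5), and, for the liberal arm, that "treatment will not be initiated until PTH rise above five times the upper limit of normal".

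**The concern.** A difference between two mean logs is the log of a ratio. It cannot be obtained by taking the log of an absolute gap, because the same gap of 4.25 is a large ratio at low PTH and a small one at high PTH. The protocol gives no arm levels from which a ratio could be formed, and 0.628 is exactly what results from taking log10 of 4.25 itself.

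Whether PTH separation can be achieved is one of the trial's stated purposes, and 0.5 times the upper normal limit is the named benchmark. The Perspective section says the trial will inform a large-scale trial. As written, the only power statement for PTH implies that 70 participants are about three times what is needed (70/22 = 3.2), and the same conversion could be carried into the next trial.

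**Working it through.** **Inputs.** From Sample size: gap 4.25, log effect 0.628, mean logPTH 1.191, SD 0.380, power 90%, alpha 0.05, drop-out 20%, 70 enrolled. From Statistics: two-sided testing. From Study design: 1:1 allocation, intensive target 2.0 to 8.5. Evaluable: 22 × 0.8 = 17.6, taken as 9 per arm; 70 × 0.8 = 56, or 28 per arm.

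**1. Reproducing 22.** The normal approximation is n per arm = 2(1.960 + 1.282)² × 0.380² / 0.628² = 7.7. The t-test needs 8.8, so 9 per arm (power 90.8%), 18 in total. Adding 20% gives 18 × 1.2 = 21.6; dividing gives 18 / 0.8 = 22.5. The stated 22 therefore comes from using 0.628 as the difference in mean log PTH.

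**2. What 0.628 is.** log10(4.25) = 0.6284, while ln(4.25) = 1.447, so the log is base 10. A log10 difference of 0.628 is a ratio of 4.25. Gap and ratio are both 4.25 only if the lower level is 4.25 / (4.25 − 1) = 1.31 and the upper is 5.56; the lower is outside the intensive target. (The target limits also have a ratio of 8.5 / 2.0 = 4.25, but their gap is 6.5, so they do not rescue the conversion.)

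**3. The correct log difference.** For an intensive-arm geometric mean x, it is log10((x + 4.25) / x), which falls as x rises. Power is from the noncentral t, two-sided 0.05, SD 0.380 in both arms:

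| Intensive level x | Liberal level | log10 difference | Power, 22 enrolled | Power, 70 enrolled | Evaluable per arm for 90% | Enrolled for 90% |
|---|---|---|---|---|---|---|
| 2.0 (floor) | 6.25 | 0.495 | 74% | 99.8% | 14 | 35 |
| 4.25 | 8.5 | 0.301 | 35% | 83% | 35 | 88 |
| 5.25 (mid-target) | 9.5 | 0.258 | 27% | 70% | 47 | 118 |
| 8.5 (ceiling) | 12.75 | 0.176 | 15% | 40% | 99 | 248 |

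The floor is the most favourable level within target. Even with all 22 evaluable (11 per arm) it gives 83%.

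**4. Which row is plausible.** Inclusion requires "Plasma PTH $>$ upper normal limit of local laboratory reference range" and/or treatment with active vitamin D or calcimetics, which is stopped for the run-in. If the liberal arm's geometric mean stays at or above 8.5 (an assumption), a gap of 4.25 is a ratio of at most 8.5 / 4.25 = 2.0. Power is then at most 35% with 22 enrolled and 83% with 70. If the liberal arm sat at the protocol's own geometric mean, 10^1.191 = 15.5, a gap of 4.25 would be 15.5 versus 11.3, a log difference of 0.139: 11% with 22 and 27% with 70.

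**5. What 70 enrolled can detect.** With 28 per arm and SD 0.380, 90% power needs a log10 difference of 0.335, a ratio of 2.16. A gap of 4.25 reaches that ratio only if x is at or below 4.25 / 1.16, about 3.65. For 80% power the figures are 0.290, ratio 1.95, and x at or below about 4.5.

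**6. Sensitivity.** The protocol gives no smaller SD and no baseline correlation, so these are assumptions:

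| Assumption | x = 2.0 | x = 4.25 | x = 5.25 | x = 8.5 |
|---|---|---|---|---|
| SD 0.30, 22 enrolled | 91% | 52% | 40% | 22% |
| SD 0.30, 70 enrolled | >99.9% | 96% | 88% | 58% |
| SD 0.380, baseline correlation 0.5, 70 enrolled | >99.9% | 92% | 82% | 50% |
| SD 0.380, baseline correlation 0.7, 70 enrolled | >99.9% | 98% | 94% | 66% |

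With 22 enrolled at x = 2.0, baseline adjustment gives 85% (correlation 0.5) or 95% (0.7). So 22 reaches 90% only near the floor, and only with an SD of about 0.30 or less or a strong baseline correlation.

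**7. Larger separations.** With 70 enrolled, 15.5 versus 5.25 (log difference 0.471) gives 99.5%, and 15.5 versus 8.5 (0.261) gives 72%.

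**The case against.** The strongest objection is to the SD. An arm truly held within 2.0 to 8.5 spans only log10(8.5 / 2.0) = 0.628, so its SD cannot exceed half of that, 0.314, and would be 0.181 if values were evenly spread. Combined with 0.380 in the liberal arm, the root-mean-square SD would be 0.349 or 0.298. Mid-target power with 70 enrolled would then be 78% or 89% rather than 70%, and at 0.298 the enrolment for 90% would be 75 rather than 118. This is fair as far as it goes: the mid-target figures are better read as a range of 70 to 89% power and 75 to 118 enrolled, with the protocol's own SD at the pessimistic end. Patients outside target would widen the spread again. It does not rescue 22, which gives about 40% at mid-target even with SD 0.30.

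It can also be said that the trial is sized on bone mineral density, that the PTH comparison is introduced as a side consideration with no formal success rule, and that the actual separation may well exceed the minimum. All of that stands and limits the consequence. But the protocol claims 90% power for exactly the 4.25 gap, and that claim is wrong as printed. Nor is it a matter for the analysis plan: the protocol states the figure.

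**Conclusion.** The concern holds. The protocol uses log10 of an absolute difference as a difference of mean logs, and its figure of 22 reproduces only with that error. At its own SD of 0.380, a two-sided 5% t-test and 20% drop-out, 22 enrolled give at most 74% power for a gap of 4.25 at any intensive-arm level of 2.0 or above, falling to 15% at the target ceiling. The 70 actually planned reach 90% only if the intensive arm is at or below about 3.65.

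These figures take 4.25 as a gap between geometric means and 0.380 as the SD in both arms. A smaller SD or baseline adjustment raises power without restoring the claim, except near the floor. The point should be fixed, but it is secondary: enrolment and the primary bone mineral density analysis are not affected.

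**What to change.** In Sample size, delete the log value of 0.628 and the figure of 22. State the sponsor's expected geometric mean PTH in each arm, the SD of log10 PTH, the resulting ratio and log10 difference, and the power that 70 enrolled (56 evaluable) give for it. If the sponsor prefers not to assume arm levels, give the detectable ratio instead, for example:

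> With 56 evaluable participants and an SD of 0.380 for log10 PTH, the trial has 90% power to detect a PTH ratio of about 2.2 between arms (80% power for a ratio of 1.95).

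Put the benchmark of 0.5 times the upper normal limit on the same scale as the analysis, either as a ratio at the stated arm levels or by back-transforming the model's arm estimates to PTH units. Report the between-group contrast with its 95% confidence interval against the benchmark on that scale.

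The cost is wording only. The stated PTH power becomes less favourable; enrolment, the primary endpoint and the planned PTH samples do not change.

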Health related quality of life will be evaluated at initiation and after 18 months through questionnaire “Kidney Disease and Quality of Life” (KDQOL-SF1.3, Danish version). The questionnaires will be sent by e-mail or e-boks from the primary investigator to the participants. If an answer has not been received after 14 days a reminder will be e-mailed. If the questionnaire has not been answered 14 days after the reminder, the research team will contact the participant by phone and ask if they need assistance for the questionnaire by the site staff or by receiving it by ordinary mail.

Visit schedule

Visit / Procedure	Visit 1 - >30 days	Visit 2 - <30 days	Visit 3 Day 0	Visit 4 1 month	Visit 5 3 months	Visit 6 6 months	Visit 7 9 months	Visit 8 12 months	Visit 9 18 months
Information	X								
Sign informed consent		X							
Randomization			X						
Screening			X						
Baseline characteristics			X						
Comorbidities, medical history, medication			X						
Standard blood samples			X	X	X	X	X	X	X
25-hydroxy vitamin D			X		X		X		X
Research biobank samples			X						X
DXA-scan			X						X
Pulse wave velocity			X						X

Hand grip strength, 10 meter walk test and sit-to-stand			X							X
Questionnaire			X							X
Bone biopsy										X*
Adverse event collection			X	X	X	X	X	X	X	X

Table 1. Visit schedule. *indicates that it is optional.

For visit 4-8 there will only be taken blood samples with follow-up by phone to minimize time consume for both patient and the investigator. Patients with CKD4-5nonD are usually scheduled in the outpatients clinic 4 times annually, investigators will try to plan the study visits on the same days.

Biobank for future research

There will be established a biobank for future research consisting of 10 ml serum and 8 ml EDTA-plasma from each patient signing the separate informed consent regarding the biobank for future research. The biobank material will be pseudonymised and kept in a locked freezer at -80°C. This is not mandatory for participating in the trial. Patients may at any time contact the primary investigator to have their plasma and serum destroyed. Analyses on the biobank material can only be performed after application and approval by the Ethics Committee System. Samples will be destroyed after 20 years.

Randomisation

Patients will be randomised in a 1:1 ratio to either the intensive PTH target group or the liberal PTH target group for an 18-month period. Randomisation will be performed within computer software.

Blinding

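### Randomisation names no stratum for prior PTH-lowering treatment, and the stated primary BMD test ignores it: a cheap improvement, not a validity flaw

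*Protocol*

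**What the plan says.** Protocol, Inclusion criteria, item 3, admits patients with PTH above the local upper normal limit "and/or treated with active vitamin D (Alphacalcidol) or calcimetics (Cinacalcet) initially". The Background frames a single comparison: "one group of patients being treated if PTH is elevated versus a second group of patients not being treated if PTH is elevated". It does not distinguish patients by earlier treatment.

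Under Interventions, after inclusion "there will be a 4 weeks run-in period where patients will not be treated with active vitamin D or calcimetics". Randomisation follows. In the intensive arm, "treatment will be initiated as soon as the PTH rise above the upper limit of normal". In the liberal arm, "treatment will not be initiated until PTH rise above five times the upper limit of normal".

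The Randomisation section reads "Patients will be randomised in a 1:1 ratio to either the intensive PTH target group or the liberal PTH target group for an 18-month period" and adds that this is done in computer software. It mentions no stratum, block or minimisation factor.

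The Sample size section applies one expected change per arm to everyone: -1.8% (SD 5.2%) for liberal and +3.1% for intensive. The latter is taken from a trial of alendronate, with the remark "We expect to obtain a similar effect in the intensive target group".

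The Statistics section compares percentage change in BMD with an unpaired t-test and supports it with an ANCOVA adjusted for baseline BMD. Under Study parameters, medication, including activated vitamin D and calcimetics, is recorded.

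**The concern.** The same PTH rule means different things for the two kinds of entrant. For a patient not treated before, with PTH between one and five times the upper limit, the arms compare starting treatment with not starting. For a patient previously on alfacalcidol or cinacalcet in the same PTH range, they compare restarting with staying off.

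The protocol's own reasoning makes it plausible that this matters. It hypothesises that suppressing PTH improves BMD, and it cites a trial in which active vitamin D gave a spine BMD difference of +4.2% after 18 months. If so, previously treated patients may reach Day 0 with part of such a gain already made and then follow a different course. The protocol gives no figure for this.

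With only 70 patients, the arms may differ by chance in the share previously treated, and nothing in the described allocation or primary test deals with that. The Perspective section also says that the trial will inform a larger one, for which results by prior treatment would be useful.

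**Working it through.** **Inputs from the protocol.** 70 randomised, so 35 per arm; 20% dropout, so 70 × 0.8 = 56 completers, 28 per arm; difference 4.9 points (3.1 + 1.8); SD 5.2; two-sided alpha 0.05; power 90%.

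**Inputs assumed, because the protocol gives none.** Share previously treated: 20-50%. Difference in 18-month BMD change between previously treated and untreated patients: g = 1 to 5 points.

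**The plan's own figure.** n per arm = 2 × (1.960 + 1.282)² × 5.2² / 4.9² = 23.7, so 24 per arm, 48 in total, and 48 / 0.8 = 60. The exact t-test needs 25 per arm, so 50 / 0.8 = 62.5, or 63. The stated 70 is not reproduced, but it errs on the safe side: 56 completers give about 94% power (93% with the t distribution). This does not affect the present point.

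**Chance imbalance.** If K of 70 patients are previously treated and 35 go to each arm, the number X in one arm is hypergeometric (70, K, 35). The between-arm gap is |X - (K - X)| / 35.

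| Share previously treated | K | SD of gap (points) | P(gap ≥ 20 points) |
|---|---|---|---|
| 20% | 14 | 9.6 | 3.4% |
| 30% | 21 | 11.0 | 11.7% |
| 40% | 28 | 11.8 | 8.7% |
| 50% | 35 | 12.0 | 15.1% |

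The probabilities do not rise steadily because patients come in whole numbers. With K = 21 or 35 a gap of exactly 7/35 = 20 points is possible. With K = 14 or 28 the smallest gap that counts is 8/35 = 22.9 points.

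**Effect on the estimate.** Shift = gap × g. For a 20-point gap:
- g = 1: 0.2 points
- g = 3: 0.6 points
- g = 5: 1.0 points

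The standard error with 28 per arm is 5.2 × √(2/28) = 1.39. The shifts are therefore 0.14, 0.43 and 0.72 standard errors, against a planned difference of 4.9. A gap of one SD (about 12 points) with g = 3 shifts the estimate by 0.12 × 3 = 0.36 points.

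**Gain from adjustment.** With share p, within-group variance = 5.2² - p(1 - p)g². For p = 0.3-0.5, power with 56 completers is 94% at g = 1 and 96% at g = 3, against 94% unadjusted. No extra patients are needed.

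**Precision by prior treatment.** Power to detect 4.9 points within a group holding 30%, 50% or 70% of the 56 completers (8.4, 14 or 19.6 per arm) is 49%, 70% or 84%. The 95% confidence interval half-widths are 5.0, 3.9 and 3.3 points. An interaction of 4.9 points has 37% power with a 30:70 split and 42% with 50:50.

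**The case against.** Several objections are sound and limit the point.

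- **A reader might infer that the missing stratum biases the trial.** It does not. Simple 1:1 randomisation is valid; chance imbalance gives no bias on average, does not inflate the type I error, and is already reflected in the standard error. It can only move the estimate in one particular trial.
- **A reader might infer that two separate trials, starting and withdrawal, have been pooled by accident.** The text does not support that. The run-in stops the drugs in both arms before randomisation, so the liberal arm does not itself withdraw them. Afterwards one threshold rule per arm applies to every entrant, in a declared pragmatic design. Restart or staying off depends on PTH after the run-in.
- **A reader might infer that the two contrasts can never be read apart without a stratum, or that stratifying separates them.** Neither holds. Medication is recorded, so results by prior treatment could be tabulated anyway, and they would be imprecise either way.
- **A reader might infer that mixing costs much power.** If the pooled effect fell to 70% or 50% of 4.9, power would drop from 94% to 69% or 42%. But nothing in the protocol says that responses differ by prior treatment, and stratifying would not restore a smaller true effect.
- **The protocol does not show that prior treatment predicts BMD change.** The +3.1% comes from a different drug and says nothing about restarting treatment. Baseline BMD is also already in the supporting ANCOVA. The point therefore rests on plausibility.
- **Covariates and subgroup tables can sit in the statistical analysis plan**, which is not at hand. That is so, but the protocol does fix an unadjusted t-test as primary. Stratified allocation cannot wait for a plan that is to be decided only before data lock, when everyone has been randomised.

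**Conclusion.** The point stands as a cheap improvement. Two kinds of entrant are admitted, no stratum is named, and the stated primary test does not use prior treatment. The trial is valid as described.

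On the assumption that 20-50% are previously treated, a gap of 20 points or more occurs in about 3-15% of trials. On the further assumption that prior treatment changes the 18-month BMD course by 1-5 points, such a gap moves the estimate by 0.2-1.0 points, always less than one standard error (1.39 with 56 completers). Both assumptions come from outside the protocol. The case for acting is that the factor is known before allocation, costs almost nothing to use, and cannot be added to the allocation later.

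**What to change.** In the Randomisation section, stratify the 1:1 allocation by one factor, treatment with active vitamin D or calcimetics at inclusion (yes/no). Use concealed permuted blocks of varying, undisclosed size. No new data are needed: medication is already looked at in pre-screening and forms part of criterion 3.

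In the Statistics section, include that factor together with baseline BMD in the BMD analysis, in place of the unadjusted t-test. Report the arm difference by prior treatment, with confidence intervals, as description only. State that these estimates are not powered and that stratification alone does not separate the two contrasts.

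Cost: one setting in the software, two allocation lists and one degree of freedom for the factor. Blocking within strata makes allocation slightly more predictable in an open-label, single-centre trial; varying undisclosed block sizes limit this but do not remove it. No patients or visits are added, and eligibility and PTH targets stay as they are.
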